7.2 Demographic and Other Baseline Characteristics

At screening, the following demographic data will be collected: date of birth, sex (gender), race, ethnicity.

Major demographic information is as follows:

1. Birth date
2. Gender
3. Race

7.2.1 Medical history

The following information will be collected for the medical history of the subjects:

Chronic Heart Failure

1. Basic information: Initial cardiovascular disease (start date, stop date/ongoing); start date of heart failure; frequency of heart failure acceleration in recent 6 month (how many times/ 6months) and how many times result to hospitalization when applicable; previous treatment procedures (PCI or CABG), time of the procedure; history of MI or not, if yes, the time need to be recorded;
2. Current medicine treatment at screening period of the study: name, dose, initiation date (month/year)

7.2.1.1 Other medical history

1. History of hypertension/ heart failure/ diabetes; the severity of these diseases; the current medicine therapy at the screening period of the study;
2. Other medical histories and concomitant medicines.

7.2.2 Vital signs and physical examination

Vital signs and physical examination should at least include the following items:

1. General status:

Heart rate (resting heart rate) measurement: sit rest for 5 minutes, no smoking, no excitatory food and beverage such as tea and coffee for 30 minutes, measurements are taken at sitting position for a continuous record of 3 minutes. Heartbeats in each minute are calculated and averaged to obtain the resting heart rate.

Blood pressure measurement: sit rest for 5 minutes, no smoking, no excitatory food and beverage such as tea and coffee for 30 minutes, measurements are taken at sitting position, with the elbow at the same level with the heart. Diastolic blood pressure is recorded at the fifth Korotkoff sound, repeated after 2 minutes and averaged. If the difference in diastolic blood pressure readings is > 5mmHg, measurement is repeated again after 2 minutes, and the 3 readings are averaged.

2. Physical examination of the respiratory system

3. Physical examination of the cardiovascular system

4. Physical examination of other systems

5. Body mass index: body weight (Kg)/Height ²(m²)

6. Measurement of waist circumference: At screening visit, under fasting, standing, calm breathing conditions, feet apart 25-30cm, waist circumference is measured at horizontal position at the midpoint of iliac spine and the 12th rib, with measuring tape close to but not press the skin, accurate to 0.1cm.

7.2.3 Lab test items

Lab examination should include at least the following items: hematological examination, and echocardiography need to be done at the screening visit and last visit; ECG need to be done at every visit.

1. Hematology tests (all these lab test need to be done by fast in the morning):

a) Full blood count: red blood cell count, neutrophils, hemoglobin, white blood cell count and platelet count

b) Liver function (ALT, AST)

c) Kidney function (BUN, Cr)

d) Fasting blood glucose

e) Blood lipid levels (TC, TG, HDL-C, LDL-C)

f) NT Pro-BNP

g) Electrolyte (K, Na)

2. Routine urine test(PH, Specific gravity, Protein, Glucose, Ketone, Nitrite, Leukocytes, Hemoglobin, Red blood cells, Bilirubin), urine pregnancy test

2. ECG: heart rate; sinus rhythm/arrhythmia, depict what kind of arrhythmia; cardiac hypertrophy (yes/no); abnormal ST-T change (yes/no);

3. Echocardiography: to measure LVEF, LVESD,LVEDD, IVST and E/A ratio

4. 6-min walk test: is a practical simple test that requires a 100-ft hallway but no exercise equipment or advanced training for technicians. Walking is an activity performed daily by all but the most severely impaired patients. This test measures the distance that a patient can quickly walk on a flat, hard surface in a period of 6 minutes.

5. SF-36 and MLHFQ: the detailed description of questionnaire test will be described in Appendix II and II.

6. Holter: Average 24 hour heart rate, average daytime heart rate, average night time heart rate, proportion of arrhythmia, proportion of 24hour heart rate >70bpm, proportion of 24hour heart rate <55bpm.

7.3 Efficacy Assessments

7.3.1 Resting heart rate

Resting heart rate obtained from the method described above.

7.3.2 Echocardiography

LVEF, LVESD, LVEDD, IVST and E/A ratio.

7.3.3 SF-36 questionnaire

The SF-36 assesses 8 health status domains (ie, physical functioning, role physical functioning, role emotional functioning, mental health, vitality, social functioning, bodily pain, and general health). Scale scores are obtained by summing the items together within a domain, dividing this outcome by the range of scores and then transforming the raw scores to a scale from 0 to 100 (See appendix II).

7.3.4 The Minnesota Living with Heart Failure Questionnaire (MLHF)

The questionnaire has 21 items. Questions assess the impact of frequent physical symptoms of heart failure - shortness of breath, fatigue, swollen ankles and difficulty sleeping. Other items ask about the effects of heart failure on physical and social functions including walking and climbing stairs, household work, need to rest, working to earn a living, going places away from home, doing

things with family or friends, recreational activities, sports or hobbies, sexual activities, eating foods he patient likes and mental and emotional functions of concentration and memory, worry, loss of self control, and being a burden to others. Since treatments might have direct effects on a patient's life in addition to their effects on symptoms and functional limitations of heart failure, questions about side effects of medications, hospital stays and costs of care were included to help measure the overall impact of treatments for heart failure on patients' quality of life.

Scoring: Simple summation of responses. Total score (min = 0, max = 105), physical dimension (min= 0, max = 40) emotional dimension (min = 0, max = 25); the higher the summed score, the worse is the impact of heart failure on a patient's quality of life (See Appendix I).

7.4 Assessment of Safety

The safety profile of the IMP will be assessed through the recording, reporting and analysis of baseline medical conditions, adverse events (AEs), physical examination findings including vital signs and laboratory tests.

Comprehensive assessment of any apparent toxicity experienced by each subject will be performed from the time of giving informed consent and throughout the trial. The investigator will report any AEs, whether observed by the Investigator or reported by the subject (see Section 7.4.1.2).

The reporting period for AEs is described in Section **Error! Reference source not found.**

7.4.1 Adverse Events

7.4.1.1 Adverse Event Definitions

Adverse Event

An adverse event (AE) is any untoward medical occurrence in a subject or clinical investigation subject administered a pharmaceutical product, regardless of causal relationship with this treatment. An AE can therefore be any unfavorable and unintended sign (including an abnormal laboratory finding), symptom, or disease temporally associated with the use of a medicinal product, whether or not considered related to the medicinal product.

For surgical or diagnostic procedures, the condition/illness leading to such a procedure is considered as the AE rather than the procedure itself.

The Investigator is required to grade the severity or toxicity of each AE.

Investigators will reference the National Cancer Institute - Common Terminology Criteria for AEs (CTCAE), version 4.0 (publication date: 28 May 2009), a descriptive terminology that can be used for AE reporting.

A general grading (severity/intensity; hereafter referred to as severity) scale is provided at the beginning of the above referenced document, and specific event grades are also provided.

If a particular AE's severity is not specifically graded by the guidance document, the Investigator is to use the general NCI-CTCAE definitions of Grade 1 through Grade 5 following his or her best medical judgment.

The 5 general grades are:

- Grade 1 or Mild
- Grade 2 or Moderate
- Grade 3 or Severe
- Grade 4 or Life-threatening
- Grade 5 or Death

According to Sponsor convention, any clinical AE with severity of Grade 4 or 5 must also be reported as an SAE. However, a laboratory abnormality of Grade 4, such as anemia or neutropenia, is considered serious only if the condition meets one of the serious criteria described above.

If death occurs, the primary cause of death or event leading to death should be recorded and reported as an SAE. "Fatal" will be recorded as the outcome of this specific event and death will not be recorded as separate event. Only, if no cause of death can be reported (for example, sudden death, unexplained death), the death per se might then be reported as an SAE.

Investigators must also systematically assess the causal relationship of AEs to IMP using the following definitions.

Unrelated: Not reasonably related to the IMP. AE could not medically (pharmacologically/clinically) be attributed to the IMP under study in this clinical trial protocol. A reasonable alternative explanation must be available.

Related: Reasonably related to the IMP. AE could medically (pharmacologically/clinically) be attributed to the IMP under study in this clinical trial protocol.

Abnormal Laboratory Findings and Other Abnormal Investigational Findings

Abnormal laboratory findings and other abnormal investigational findings (for example, on an ECG trace) should not be reported as AEs unless they are associated with clinical signs and symptoms, lead to treatment discontinuation or are considered otherwise medically important by the Investigator. If a laboratory abnormality fulfills these criteria, the identified medical condition (for example, anemia, increased ALT) must be reported as the AE rather than the abnormal value itself.

- **Adverse Reaction(ADR)**

In accordance with GCP, adverse drug reaction is an adverse event considered related to drug treatment.

Serious Adverse Event

A serious adverse event (SAE) is any untoward medical occurrence that at any dose:

- Results in death.
- Is life-threatening.

NOTE: The term “life-threatening” refers to an event in which the subject is at risk of death at the time of the event; not an event that hypothetically might have caused death if it was more severe.

- Requires inpatient hospitalization or prolongation of existing hospitalization.
- Results in persistent or significant disability/incapacity.
- Is a congenital anomaly/birth defect.
- Is otherwise considered as medically important.

Note: Important medical events that may not result in death, be life-threatening, or require hospitalization may be considered as SAEs when, based upon appropriate medical judgment, they may jeopardize the subject or may require medical or surgical intervention to prevent one of the outcomes listed above. Examples of such events include allergic bronchospasm requiring intensive treatment in an emergency room or at home, blood dyscrasias or convulsions that do not result in inpatient hospitalization, or the development of drug dependency or drug abuse.

For the purposes of reporting, any suspected transmission of an infectious agent via an IMP is also considered a SAE as described in Section 7.4.1.4.

Events that Do Not Meet the Definition of an SAE

Elective hospitalizations to administer, or to simplify trial treatment or trial procedures (for example, an overnight stay to facilitate chemotherapy and related hydration therapy application) are not considered as SAEs. However, all events leading to unplanned hospitalizations or unplanned prolongation of an elective hospitalization (for example, undesirable effects of any administered treatment) must be documented and reported as SAEs.

Events Not to Be Considered as AEs/SAEs

Medical conditions present at the initial trial visit that do not worsen in severity or frequency during the trial are defined as Baseline Medical Conditions, and are NOT to be considered AEs.

However, if adverse signs or symptoms occur in association with disease progression then these should be recorded as AEs.

7.4.1.2 Methods of Recording and Assessing Adverse Events

At each trial visit, the subject will be queried on changes in his/her condition. During the reporting period of the trial any unfavorable changes in the subject's condition will be recorded as AEs, whether reported by the subject or observed by the investigator.

Complete, accurate and consistent data on all AEs experienced for the duration of the reporting period (defined below) will be reported on an ongoing basis in the appropriate section of the CRF. Among these AEs, all SAEs or non-serious ADRs must be additionally documented and reported using an Adverse Event Safety Report Form as described in Section 7.4.1.4.

It is important that each AE report include a description of the event, its duration (onset and resolution dates [and times, when it is important to assess the time of AE onset relative to the recorded treatment administration time]), its severity, its causal relationship with the trial treatment, any other potential causal factors, any treatment given or other action taken (including dose modification or discontinuation of the IMP) and its outcome. In addition, serious cases should be identified and the appropriate seriousness criteria documented. If an AE constitutes a DLT this has to be documented accordingly

Specific guidance can be found in the CRF Completion and Monitoring Conventions provided by the Sponsor.

7.4.1.3 Definition of the Adverse Event Reporting Period

The adverse event reporting period for safety surveillance begins when the subject is included in the trial (date of first signature of informed consent) and continues until the 30-Day Post-Treatment Safety Follow-up.

Any SAE assessed as related to IMP must be reported whenever it occurs, irrespective of the time elapsed since the last administration of IMP.

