LVEF	Left ventricular ejection fraction
LVEDD	left ventricle end-diastolic dimension
LVESD	left ventricular end-systolic dimension
MLHFQ	Minnesota Living with Heart Failure Questionnaire
NDHP- CCBs	Non-dihydropyridine calcium channel blockers Pharmacodynamics
NTPro-BNP	N-terminal Pro-B-type Natriuretic Peptide
NYHA	New York Heart Association

PGx	Pharmacogenetics/Pharmacogenomics
PK	Pharmacokinetics
SAE	Serious Adverse Event
SBP	Systolic Blood Pressure

[figure not shown]

1 Synopsis

Clinical Trial Protocol Number	MS200006-0039
Title	A single-arm, interventional, multi-center, pilot study to evaluate the efficacy of oral Bisoprolol on heart rate reduction in Chinese Chronic Heart Failure patients with NYHA class II – IV (Biso-CHF Study)
Trial Phase	IV
IND Number	Not applicable
FDA covered trial	No
EudraCT Number	Not applicable
Coordinating Investigator	PPD [Redacted]
Sponsor	Merck Serono Co.,Ltd [name]
Sponsor Legal Representative in the European Union	Not applicable
Trial centers/countries	10 (Center)/1 (country)
Planned trial period (first subject in-last subject out)	Dec, 2016 – Oct, 2018
Trial Registry	www.clinicaltrials.gov (in process)

Objectives:
 
Primary objectives
 
To explore the heart rate control under different doses of Bisoprolol in Chinese Heart Failure patients with NYHA class II- IV
 
Secondary Objectives
 
To explore other efficacy parameters and safety profile of Bisoprolol treatment in Chinese Heart Failure patients
	

Methodology: A single-arm, interventional, multi-center pilot study to evaluate the efficacy of different dose of oral Bisoprolol on heart rate reduction in Chinese Chronic Heart Failure (CHF) patients with New York Heart Association (NYHA) class II – IV. 236 eligible CHF patients will be enrolled and given oral Bisoprolol up-titration treatment from 1.25mg to 2.5mg,
	

3.75mg, 5mg, 7.5mg and 10mg during 26 weeks treatment period. For all the patients, 6-mins walk test and Questionnaires will be tested at both screening period and end of treatment. Other laboratory parameters will be collected at Screening, 6 weeks, 14 weeks and 26 weeks of treatment. There will be 8 visits from the beginning to the end of the study.

Planned number of subjects: 236

Primary endpoints: Resting heart rate under 2.5mg (6±2weeks), 5mg (14±2weeks) and 10mg (26±2weeks) of Bisoprolol vs at baseline

Secondary endpoints:

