5.1.1 Major aspects of the trial

There will be a 2-week screening period when baseline lab tests, electrocardiogram (ECG), ultrasound cardiogram (UCG), Holter and Questionnaires will be conducted in this period. Patients who met all the inclusion criteria but none of the exclusion criteria will be enrolled. Totally 236 patients will be enrolled in the study. The anticipated period of the whole study is approximately 21 months including a 14-month recruitment period and a 26-week treatment period.

All enrolled patients will start to take oral Bisoprolol 1.25mg, once daily. All other cardiovascular medicines must be stabilized at least one month before screening period and could be continued. There will be 8 visits in total. Oral Bisoprolol needs to be started from 1.25mg (3±1weeks), up-titrated to 2.5mg (6±2weeks), 3.75mg (10±2weeks), 5mg (14±2weeks), 7.5mg (18±2weeks) with an interval of 3-4 weeks, then up-titrated to 10 mg after 8 weeks (26±2weeks). Symptoms, ECG and safety endpoints will be assessed at all visits. Lab tests will be assessed at 2.5mg (6±2weeks), 5mg (14±2weeks) and 10mg (26±2weeks). Please refer to Figure 1 for a detailed study diagram.

The Up-titration should be judged by the investigator and patients must well tolerate the previous dose. Intolerance may be defined as:

- (1) Resting heart rate < 55bpm;
- (2) Blood pressure < 90/50 millimetre(s) of mercury(mmHg);
- (3) Adverse Event (AE) lead to intolerance as judged by the investigator;

The primary endpoint is:

Resting heart rate under 2.5mg (6±2weeks), 5mg (14±2weeks) and 10mg (26±2weeks) of Bisoprolol vs at baseline

The secondary endpoints include:

- Resting heart rate at 1.25mg (3±1weeks), 3.75mg (10±2weeks), and 7.5mg (18±2weeks) vs at baseline
- Heart function detected by UCG: including LVEF, left ventricular end-systolic dimension (LVESD) and left ventricle end-diastolic dimension (LVEDD), interventricular septal thickness (IVST) and E/a ration at baseline, 5mg (14±2weeks) and 10mg (26±2weeks).
- Systolic and diastolic blood pressure, symptoms and NYHA classification at all visits.

- Proportion of patient number whose Resting heart rate < 70 and > 55 bpm at all visits
- Quality of life [based on the MOS item short form health survey (SF-36) and Minnesota Living with Heart Failure (MLHFQ)] at baseline and end of treatment.
- 6-minute walk test and N-terminal Pro-B-type Natriuretic Peptide (NT Pro-BNP) at baseline and end of treatment.

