5.7 Definition of End of Trial

A clinical trial protocol may not be considered closed as long as:

- Any subject is still receiving any IMP,
- Visits specified by the protocol are still taking place,
- Procedures or interventions according to the protocol are still being undertaken in any subject,
- The post-treatment follow up period, defined in the clinical trial protocol as being part of the trial, has not yet been completed for any subject.

6 Investigational Medicinal Product and Other Drugs Used in the Trial

The term “Investigational Medicinal Product” refers to an active substance or a placebo being tested or used as a reference therapy in a clinical trial, including products that have a marketing authorization but are formulated, packaged, or administered differently from the authorized form, used for an unauthorized indication, or used to gain further information about the authorized form.

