7.4.1.6 Monitoring of Subjects with Adverse Events

AEs are recorded and assessed continuously throughout the trial (see Section **Error! Reference source not found.**) and are assessed for final outcome at the 30-Day Follow-up Safety Visit. All SAEs ongoing at the 30-Day Follow-up Safety Visit (note any other type or category of AE to be followed up) must be monitored and followed up by the Investigator until stabilization or until the outcome is known, unless the subject is documented as “lost to follow-up”. Reasonable attempts to obtain this information must be made and documented. It is also the responsibility of the Investigator to ensure that any necessary additional therapeutic measures and follow-up procedures are performed.

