7.4.2 Pregnancy and In Utero Drug Exposure

Pregnancies are not considered per se to be adverse events. However, all pregnancies with an estimated conception date during the period defined in Section 7.4.1.3 must be recorded by convention in the AE page/section of the CRF. The same rule applies to pregnancies in female subjects and to pregnancies in female partners of male subjects. The Investigator must notify the Sponsor in an expedited manner of any pregnancy using the Pregnancy Report Form, which must be transmitted according to the same process as described for SAE reporting in Section 7.4.1.4.

Investigators must actively follow up, document and report on the outcome of all these pregnancies, even if the subjects are withdrawn from the trial.

The Investigator must notify the Sponsor of these outcomes using the Pregnancy Report Form, and if an abnormal outcome occurs, the SAE Report Form if the subject sustains an event and the Parent-Child/Fetus Adverse Event Report Form if the child/fetus sustains an event.

Any abnormal outcome must be reported in an expedited manner as described in Section 7.4.1.4, while normal outcomes must be reported within 45 days from delivery.

In the event of a pregnancy in a subject occurring during the course of the trial, the subject must be discontinued from trial medication immediately. The Sponsor must be notified without delay and the subject must be followed as mentioned above.

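### The AE reporting period ends at a 30-day post-treatment safety follow-up that the 8-visit schedule does not contain

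*Combined protocol and SAP*

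**What the plan says.** Two safety sections depend on a contact about 30 days after treatment. Section 7.4.1.3 starts the AE reporting period at consent and says that it "continues until the 30-Day Post-Treatment Safety Follow-up". Section 7.4.1.6 says that AEs "are assessed for final outcome at the 30-Day Follow-up Safety Visit". It also uses that visit to decide which ongoing SAEs must be followed further. Section 7.4.2 ties pregnancy recording to the same window: "all pregnancies with an estimated conception date during the period defined in Section 7.4.1.3 must be recorded".

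The schedule stops earlier. The Synopsis states: "There will be 8 visits from the beginning to the end of the study". Section 5.1.1 repeats the count of 8. Section 7.1 describes Visits 1 to 8 and ends at week 26±2. Appendix III has no column after Visit 8, and its AE row ends there. The Synopsis gives a single figure of 26 weeks for trial and treatment duration per subject, which leaves no post-treatment period.

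Section 7.4.1.2 links active AE questioning to visits: "At each trial visit, the subject will be queried on changes in his/her condition".

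**The concern.** Sites usually work from the visit schedule. If the schedule has no 30-day contact, nothing in it prompts the site to ask the patient about that month or to close out ongoing AEs. The end of the reporting period would then be covered only by what patients or other clinicians happen to report. Sites that read Section 7.4.1.6 closely would make the contact and others would not, so ascertainment could differ across the 10 sites.

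At stake are mainly non-serious unrelated AEs that start after Visit 8, unrelated SAEs that the site never hears of, some final AE outcomes, and conceptions in those 30 days.

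**Working it through.** No power or precision calculation applies. The check is a comparison of sections and a count of days.

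**1. Visit count.** Section 7.1 lists Visits 1 to 8. Appendix III has 8 visit columns. Both agree with the 8 stated in the Synopsis and Section 5.1.1. None falls after week 26±2.

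**2. Where the 30-day contact would fall.** Section 7.1 sets Day 0 as the first day of dosing. Assume that the last dose is at Visit 8.
- Visit 8: 26 × 7 = day 182; window 24 × 7 = 168 to 28 × 7 = 196.
- Thirty days later: 182 + 30 = day 212; range 168 + 30 = 198 to 196 + 30 = 226.
- In weeks: 212/7 = 30.3; range 198/7 = 28.3 to 226/7 = 32.3.

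The contact would therefore be a ninth one, at about week 30. On this assumption even the latest permitted Visit 8 (week 28) comes before the earliest possible follow-up (week 28.3), so Visit 8 cannot double as the 30-day visit for a patient who is dosed up to Visit 8.

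**3. Patients who stop early.** Sections 5.5, 5.5.1, 6.5.2 and 6.5.3 give many reasons for withdrawal, but none schedules a contact after the last dose. At the 15% dropout assumed in Section 8.1, this is 0.15 × 236 = 35.4, or about 35 patients. Some of them may not be contactable.

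**4. What still works without the contact.** Section 7.4.1.4 requires SAEs and non-serious adverse drug reactions to be reported within 24 hours of awareness during the reporting period. Section 7.4.1.3 requires related SAEs to be reported whenever they occur. Both depend on the site learning of the event. Neither replaces active questioning or the final-outcome assessment.

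**5. What is not touched.** The primary endpoints are resting heart rate at weeks 6, 14 and 26 against baseline (Section 8.3.1). All are measured by Visit 8.

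**The case against.** The strongest reply is that the 30-day wording may be left over from a template. The safety and administrative text carries other such remnants: a mention of dose-limiting toxicity in Section 7.4.1.2, a chemotherapy example in Section 7.4.1.1, an unfilled placeholder in Section 6.13, and a drafting note inside the Section 7.4.1.6 sentence on ongoing SAEs. The trial-specific text consistently gives 8 visits and 26 weeks. This stands as far as intent goes: the documents do not show whether the schedule omits a planned visit or the safety text names an unplanned one. It does not remove the contradiction, because both texts are operative.

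A second reply is that sites are bound by the whole protocol, and that the Manual of Operations or the CRF conventions, which are not in these documents, may cover the contact. That is why the consequence is stated as possible and not as certain.

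Several stronger readings are tempting, but the documents do not support them.
- **That the study length proves that a visit was forgotten.** Section 5.1.1 says: "The anticipated period of the whole study is approximately 21 months including a 14-month recruitment period and a 26-week treatment period". At 30.44 days per month, 14 months + 26 weeks is 14 + 182/30.44 = 20.0 months, and 30 more days gives 14 + 212/30.44 = 21.0. But 14 days of screening and Visit 8 at week 28 give 14 + (14 + 196)/30.44 = 20.9 months with no follow-up at all. The figure does not discriminate.
- **That the end-of-trial definition settles it.** Section 5.7 keeps the trial open for "The post-treatment follow up period, defined in the clinical trial protocol as being part of the trial". This may be generic wording, and it does not itself create such a period.
- **That the broken cross-reference causes the omission.** The sentence in Section 7.4 that begins "The reporting period for AEs is described in Section" has lost its target. But Section 7.4.1.2 says that the period is defined below it, the next heading is that definition, and Section 7.4.2 cites 7.4.1.3 by number.
- **That about 13% of AEs are lost.** With 14 days of screening, 30/(14 + 182 + 30) = 30/226 = 13.3%. This is a share of calendar time and says nothing about the share of events.
- **That deaths or heart-failure readmissions are under-counted.** Nothing in the documents shows this.

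**Conclusion.** The protocol is internally inconsistent on whether a 30-day post-treatment safety contact takes place. Confidence in the mismatch is high, because it rests on the text alone. Which side was intended is not established.

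The size is one contact per patient, for at most 236 patients, and a final 30 days of the reporting period without scheduled questioning. How many events would be missed cannot be estimated from these documents. That a site would miss the contact rests on the assumption that it works from the schedule and that no operational document fills the gap. The effect is confined to safety ascertainment and its consistency across sites. The point should be corrected, but it does not threaten the primary result.

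**What to change.** **Preferred.** Add a safety contact 30 days after the last dose to Section 7.1 and Appendix III; a telephone call is enough. Apply it to completers, and to patients who stop early where contact is possible. Record new AEs and SAEs, outcomes of ongoing AEs, and pregnancies. Correct the visit count in the Synopsis and Section 5.1.1, and change the per-subject duration to 26 weeks of treatment plus 30 days of follow-up.

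**Alternative, if the 30-day text was not intended.** Amend Sections 7.4.1.3 and 7.4.1.6 so that the reporting period and the final-outcome assessment end at Visit 8 or last dose. The pregnancy window in Section 7.4.2 then shortens with them. This removes the contradiction but gives less safety information.

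**Cost.** The preferred fix needs one brief call per patient, one schedule column, one CRF page and a protocol amendment submitted to the ethics committee. Under Section 10.5, renewed consent is needed if the change could affect a patient's agreement to participate. The alternative needs only the amendment and text edits.

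Whether events in the 30-day window count as treatment-emergent is a separate, minor point, which can be settled in Section 8.5.4 in the same amendment.
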